International and Ukrainian institutions have made significant commitments to increasing the quality of HIV/AIDS services, strengthening the capacity of Ukrainian institutions to improve the continuum of HIV services for key populations, and improving access to MAT. USAID and PEPFAR both currently support efforts to improve HIV case finding, primarily through increased HIV testing and initial linkage to care. Moreover, Ukraine has expanded availability of and access to MAT, a critical component of successful retention and care for PWID.^{20-23,44-48} Our proposed D2C strategy complements these efforts and leverages the expansion of MAT in Ukraine by identifying out-of-care HIV-positive PWID and linking them with HIV and other services, including MAT. The D2C intervention would be a valuable amendment that would increase the cost-benefit ratio of any case-management intervention by timely identifying patients who need it most.

A planning grant (R34) is the ideal mechanism for this developmental project. It will allow the research team to establish the feasibility of a D2C for PWID in Ukraine and develop the tools, protocols, and management structure for implementing a full-scale trial. It will also produce important planning information on the cost of implementing a D2C in Ukraine and allow us to determine under what conditions a D2C may be a reasonable investment in Ukraine. Finally, the proposed analytic strategy will inform sample size estimation for a larger trial and determine whether ordinal logistic regression, and more specifically mixed proportional odds models, may be suitable for modeling movement along the HIV care continuum among PWID.

The **scientific premise** of this project is strong. Only 29% of HIV-infected PWID in Ukraine are virally suppressed; of PWID who are on ART, only about 74% are undetectable.⁴⁹ Connecting PLWH who are diagnosed to comprehensive case management and ancillary services can improve outcomes along the HIV care continuum. Clinical and service provision data, including viral suppression, ART prescription, medical visits, and engagement in other services, can be used to improve health outcomes for HIV-positive PWID. This D2C intervention extends current efforts to improve the availability and use of data by assessing clients with standardized, validated assessments on a range

D2C Ukraine

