Finalize the d2c strategy The finalization activities will include: (1) refining data extraction protocols and developing a case management module within the MIS; (2) developing a report generation and dissemination protocol for each clinic and (3) specify clinic/implementation team structure, roles, and management plans based on findings from in-depth interviews.

Develop data extraction protocols and create case management module within MIS

The MIS is designed as an electronic medical record system, to be used by clinical providers for routine patient data management. It has centralized architecture, where all data are immediately uploaded to a national-level server. According to the feedback we received in our ART OPTI project, tracking and prioritization of out-of-care patients is one of the most requested features for the MIS. We will partner with the Public Health Center of the MoH, the government body responsible for HIV response and coordination of PEPFAR activities in Ukraine and owner of the MIS to create a module within the MIS that will: a) identify all HIV-positive PWID meeting the criteria of not-in-care [patients registered as HIV-positive who had no HIV medical visits in a calendar year]; b) provide a useful summary of all clinical information that will be needed for case managers [drug use, CD4, viral load, ART history, HIV care appointments made and kept, co-morbid diagnoses and medications, and MAT history]; and c) provide a portal for entry and export of case management data (referrals made, appointments kept, contact attempts, case management notes).

Specific Aim 2: To pilot a randomized clinical trial of a D2C strategy versus standard of care

Study Design

[figure not shown]
This pilot study is designed to test the performance characteristics and capabilities of study design, measures, procedures, recruitment criteria, and operational strategies that are under consideration for use in a prospective RCT. We will also assess feasibility of the RCT by measuring the key parameters for sample size calculation, namely the effect size and coefficient of variation.

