D2C is a structural intervention designed to sustainably change the HIV care providers' practices and facilitate information exchange at the facility level. To address the implementation science questions by measuring the provider-level outcomes and avoid contamination of the control condition due to unblinded allocation of intervention at the patient level, we propose a cluster-randomized trial design for this pilot study and the prospective RCT. We will select eligible HIV clinics (see "Study Sites," above) and randomly assign them 1:1 either to the intervention or the control arms. To achieve greater comparability between the arms, we will match pairs of eligible sites based on organizational context factors derived from Aim 1 data analysis, including facility size and type (e.g., NGO vs. public clinic), service delivery structure (e.g., social workers vs. nurses), and existing services for HIV-positive PWID (e.g. Steps Toward Health) and will randomize within the pairs. This will minimize the degree of between-cluster variation within the groups and increase power and precision.

Randomization will be conducted by the data manager using a computer program.

Sample size

We used methodology from Hayes et al⁸⁴ to determine the effect size that the intervention needs to demonstrate in a feasible matched-pair randomized trial. We assumed the cluster size of 75 patients (based on the optimal case manager workload) with 5 clusters per arm (potentially manageable number given the existing research infrastructure in Ukraine), coefficient of variation between clusters within matched pairs equal to 0.15 (empirically estimated based on the data from 56 clinics in the ART OPTI study, see Previous Studies), power of 80% and 0.05 significance level. Proportion of participants re-engaging into ART within 3 months after inclusion into the study was used as the key outcome. Under the assumptions, the relative difference between the study arms should be at least 22% (e.g. 50% vs 72%). The adjacent chart shows the power and sample size of a pilot trial needed to detect this difference with 0.05 significance level. To achieve 80% power, we will need to recruit 160 participants, or 80 per arm. We propose to divide the sample equally between 4 sites (2 per arm) to test the matching procedures. We do not adjust for loss-to-follow-up because for our main outcomes (ART initiation, viral suppression), loss to follow-up is equal to not achieving the outcome.

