We have powered this pilot study to evaluate feasibility of a prospective cluster RCT. The RCT will be considered feasible if the difference in the proportion of patients achieving the primary outcome (engagement in HIV care) will reach 22% between the study arms. We will estimate the impact of the intervention on the HIV care continuum using mixed effects models. For all outcomes, the data will have the same structure, with observations (t) nested within participants (i) nested within sites (j) nested within matched pairs (k). The correlations among observations will be addressed by using fixed-effects indicators for matched pair and normally distributed random intercepts for sites and for participants. Our mixed-effects models will include indicators for each of the two follow-up assessments, an indicator for site group assignment, and two group-assignment-by-follow-up interaction terms. We will also include sex/gender, age, and baseline covariates that have been identified in preliminary analyses as varying significantly across sites. A logit link function will be used for the primary outcome of ART (re-)initiation (defined above), and the coefficients for the two group-assignment-by-follow-up interaction terms will provide the estimates of the subject-specific intervention effects at 6 and 12 months post-baseline. We will examine the effects of sex/gender, age, substance use severity, ART history at baseline and other covariates in the multivariable models.

We will characterize patterns of behavior that impact HIV transmission (episodes of syringe sharing and episodes of unprotected intercourse in the prior 30 days without viral suppression) and we will use the same mixed-effects approach described above but with a log link function and negative

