binomial distribution. These analyses will provide parameters for estimating the rate of onward HIV transmission for the cost-threshold analysis. All analyses will include the use of the mixed effects "meqrlogit," "meologit," and "menbreg" procedures using Huber/White robust variance-covariance estimators. We will examine whether missingness is associated with observed data using standard methods.^{98–100} We will conduct a second set of outcome analyses using multiple imputation to evaluate the robustness of the primary outcome analyses to missingness and report estimates based on multiple imputation that would be valid based on the assumption that the data are missing at random (MAR). We will produce imputed datasets ($m > 10$) using chained equations,¹⁰¹ run outcome analyses on all sets, and derive point and standard error estimates for treatment effects and other parameters from the distribution of estimates from the outcome analyses with imputed datasets.

We will also evaluate the use of mixed proportional odds regression^{102,103} for determining whether intervention exposure is associated with an individual's location on five distinct stages of HIV care continuum: (1) not engaged in HIV care in the prior six months; (2) engaged in HIV care in the prior six months but no ART use in the prior 30 days; (3) ART use in the prior 30 days but no evidence of viral suppression in the prior 6 months; and (4) ART use in the prior 30 days with evidence of viral suppression in the prior 6 months. The HIV care continuum can be viewed as an ordinal categorical variable, and ordinal logistic regression will be used to evaluate if group assignment is associated with the location along the HIV care continuum. We will use the Score test to evaluate whether the proportional odds assumption of ordinal logistic regression.¹⁰⁴

These analyses will be essential for planning a full study. The findings will be used for sample size estimates, and data on HIV transmission risk will be used to determine whether the intervention could reasonably be cost-saving or cost-effective. This pilot analysis will provide important information on the feasibility of using ordinal logistic regression in a larger trial or in other analyses of the HIV care continuum.

Specific Aim 3a: To assess the feasibility, acceptability, and implementation-related processes and outcomes of the D2C strategy

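### Nothing stops the full trial from being sized on a pilot effect estimate that is kept only when it reaches 22 points and is therefore inflated

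*Combined protocol and SAP*

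**What the plan says.** Three places link the pilot to the size of the full trial. Specific Aim 2, Study Design, says feasibility will be assessed by "measuring the key parameters for sample size calculation, namely the effect size and coefficient of variation". Statistical Analysis and Feasibility Assessment closes with "The findings will be used for sample size estimates". The Background adds that "the proposed analytic strategy will inform sample size estimation for a larger trial". Only the first of these names the effect size.

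Statistical Analysis and Feasibility Assessment also sets the condition for going ahead, in a sentence that begins "The RCT will be considered feasible if the difference in the proportion of patients". The outcome it names is engagement in care, and the bar is 22%. The threshold applies to the observed difference.

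The Sample size section is the origin of the 22 points. It takes 5 clusters per arm of 75 patients, a CV of 0.15 within matched pairs, and "power of 80% and 0.05 significance level". It concludes that "the relative difference between the study arms should be at least 22% (e.g. 50% vs 72" per cent). The word there is relative, but the example is an absolute 22 points. The outcome in that calculation is ART re-engagement within 3 months. The feasibility threshold is on engagement in care, which Data Collection defines over 12 months. For the pilot: "To achieve 80% power, we will need to recruit 160 participants, or 80 per arm", spread over four sites.

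**The concern.** An estimate that is used only when it is large overstates the truth on average. Here the pilot estimate must reach 22 points before the full trial is launched, and the effect size is listed among the quantities the pilot supplies for sizing. With four clinics and 160 patients, the standard error is about half the threshold, so the overstatement is not small. A trial sized on the surviving estimate would have too few clinics for the effect that is really there. Preparing that larger trial is a main purpose of this planning grant.

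**Working it through.** **Inputs from the protocol.** 50% vs 72%; 80 per arm; 4 sites (40 each, 2 per arm); 75 per cluster in the full trial; CV 0.15; alpha 0.05; power 80%; threshold 22 points.

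**Assumptions not in the protocol.** Two-sided test; 50% control proportion also for the threshold outcome; full trial sized by the matched Hayes–Bennett formula; CV 0 and 0.25 as a range for the pilot.

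**1. The pilot's own figure.** With pooled proportion 0.61, n per arm = [1.96√(2·0.61·0.39) + 0.842√(0.25 + 0.2016)]² / 0.22² = 76. At 80 per arm, power is 82%. A 22-point difference at maximum variance (39% vs 61%) gives exactly 160 in total. So 160 reproduces as an individually randomised calculation without clustering.

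**2. The protocol's full-trial figure.** V₇₅ = p₀q₀/75 + p₁q₁/75 + CV²(p₀² + p₁²) = (0.25 + 0.2016)/75 + 0.0225(0.25 + 0.5184) = 0.0233. Then 7.849 × 0.0233 / 0.22² = 3.8. Adding 1 (unmatched) gives 4.8, which matches the stated 5 clusters per arm. Adding 2 (matched pairs) gives 5.8, so 6 pairs.

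**3. Precision of the pilot at a true 22 points.** V₄₀ = (0.25 + 0.2016)/40 + 0.0225 × 0.7684 = 0.0286. SE = √(V₄₀/2) = 0.1195. With CV 0 it is 0.075.

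**4. Effect of the threshold.** For true difference d, let a = (0.22 − d)/SE. The mean estimate given a pass is d + SE·φ(a)/(1 − Φ(a)). At d = 0.22, a = 0 and φ(0)/0.5 = 0.798:
- CV 0.15: 0.22 + 0.1195 × 0.798 = 0.315
- CV 0: 0.22 + 0.075 × 0.798 = 0.280

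A simulation of 400,000 pilots per scenario gave 31.3 and 27.9 points, with 51% of pilots passing in each case. At CV 0.25 it gave 34.7.

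**5. Consequence at a true 22 points, CV 0.15.** Sizing on 0.315: V₇₅ = 0.0259, and pairs = 2 + 7.849 × 0.0259/0.315² = 4.05, rounded up to 5. Power of 5 pairs at the true 22 (noncentral t, 4 df) is 68%. If each passing pilot instead sizes its own trial, so that the planned number varies, mean power is about 63% by the normal approximation and 61% by noncentral t. Sizing on 22 points itself gives 6 pairs and 80%. Using pilot estimates without the threshold gives about 78%, so most of the loss comes from the selection.

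**6. Smaller true effects, CV 0.15.** Each row shows the pilot result, the pairs planned on the mean passing estimate, and power at the true effect.

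| True difference | Pilots passing | Mean estimate if passed | Pairs planned | Power | Power of the protocol's 5 × 75 design | Power with 6 pairs |
|---|---|---|---|---|---|---|
| 10 | 15% | 28 | 5 | 23% | 23% | 29% |
| 15 | 27% | 29 | 5 | 42% | 42% | 52% |
| 22 | 50% | 32 | 5 | 68% | 68% | 80% |

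The sixth column uses no pilot estimate at all, yet equals the fifth. The low powers at 10 and 15 points therefore come mostly from the gap between those effects and the 22-point target.

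**7. Larger true effects (simulation).** At 25 points and CV 0.15, mean power is about 71%. At 30 points it is 79% (84% at CV 0), and the loss has largely gone.

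**8. Different outcomes.** If the threshold is on one outcome and sizing on another, the inflation scales with the correlation of the two estimates. At a true 22 and CV 0.15 it is 9.4 points at correlation 1, 6.6 at 0.7 and 3.8 at 0.4.

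**The case against.** The Sample size section can be read as working backwards. It starts from a manageable trial of 5 clusters of 75 per arm, derives the effect the intervention must show, and has the pilot ask whether that effect is reached. On this reading the pilot estimate is compared with a pre-set detectable difference, and the full trial is never shrunk to fit an estimate of about 30 points. That reading is coherent, and nothing in the protocol rules it out. It does not fit easily with the Study Design sentence, which names the effect size as a parameter for the sample size calculation.

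Three stronger readings are tempting, and the documents support none of them.
- A reader might infer that the full trial will be sized on the raw pilot estimate. The protocol never says so.
- A reader might infer that the very estimate that passes the threshold feeds the sizing. The threshold outcome is 12-month engagement, while the only sizing outcome named is 3-month ART re-engagement. If they stay different, the inflation shrinks but remains unless the two estimates are uncorrelated.
- A reader might infer that the full trial will be underpowered, and cite 23% or 42% power as damage from selection. Those figures equal the power of the existing 5 × 75 design, and at a true 30 points the shortfall largely disappears.

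**Conclusion.** The point holds in conditional form. The protocol lists the pilot effect size as an input to sizing, makes the full trial depend on an observed 22-point difference, and adds no protection for the planning effect. If the estimate that passed is used for sizing, its mean at a true 22 points is about 31 to 32 (about 28 at CV 0). The loss attributable to this at a true 22 is from about 80% power to about 61–68%. These figures rest on a 50% control proportion for the threshold outcome, four clinics of 40, a two-sided test, the matched formula with 75 per cluster and CV 0.15 for the full trial, and the same outcome for threshold and sizing.

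**What to change.** In Specific Aim 2, Study Design, remove the effect size from the parameters the pilot supplies for sizing the full trial. State there, and in Statistical Analysis and Feasibility Assessment, that the full trial will be sized on a target absolute difference fixed in the protocol before pilot data are seen, on one named outcome. The target can be the 22 points of the Sample size section or a smaller difference with a justification. Use the pilot for the control-arm proportion, enrolment yield and retention. Report its effect with a confidence interval, as descriptive.

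The cost is protocol wording, with no extra patients, sites or data in the pilot. The team has to commit to a target in advance, and the full trial may be slightly larger: about 6 pairs at 22 points under the matched formula, not 5. A smaller target would need more, which has to be weighed against the protocol's view of how many clusters are manageable.

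### Two matched pairs leave 1 degree of freedom for between-clinic variance, so the pilot cannot usefully measure the coefficient of variation it promises for sizing the RCT

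*Combined protocol and SAP*

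**What the plan says.** Specific Aim 2, Study Design, names two quantities that the pilot will supply for the later trial: "measuring the key parameters for sample size calculation, namely the effect size and coefficient of variation". After the outcome models, Statistical Analysis and Feasibility Assessment says: "The findings will be used for sample size estimates".

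The design is in Study Design and Sample size. Clinics are matched, and the investigators "will randomize within the pairs", allocating 1:1. On numbers: "We propose to divide the sample equally between 4 sites (2 per arm) to test the matching procedures". That is two pairs with 40 patients per clinic (160/4).

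The analysis model uses "fixed-effects indicators for matched pair and normally distributed random intercepts for sites and for participants", with an indicator for arm.

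Sample size already contains a within-pair CV of 0.15, described as "empirically estimated based on the data from 56 clinics in the ART OPTI study". No section gives an estimation method, interval or precision target for the pilot CV, or says how it would be combined with the 0.15.

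**The concern.** In each pair, one clinic has the intervention and the other does not. The difference between them mixes the intervention effect with ordinary clinic-to-clinic variation. The two can be separated only by seeing how the pair difference varies from pair to pair, and there are two pairs.

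The required number of clusters depends strongly on the CV. If the pilot estimate were taken at face value, the RCT could be planned far too small or several times too large. An estimate of zero is the likeliest single result. It would look reassuring and would point to a small trial.

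**Working it through.** **Inputs.** From Sample size: 50% vs 72%, 75 patients per RCT cluster, within-pair CV k = 0.15, 80% power, 0.05 significance (two-sided assumed; sidedness is not stated), four pilot sites, 160 patients. From the statistical section: the model above.

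**1. The plan's own RCT figure.** The Hayes-Bennett formula for clusters per arm is

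c = a + (1.96 + 0.84)² × [p0(1−p0)/m + p1(1−p1)/m + k²(p0² + p1²)] / (p1 − p0)²,

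with a = 1 unmatched, a = 2 matched, and the squared term equal to 7.849 (unrounded z values). With m = 75:

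- binomial part: (0.25 + 0.2016)/75 = 0.00602
- between-clinic part: 0.0225 × (0.25 + 0.5184) = 0.01729
- 7.849 × 0.02331/0.0484 = 3.78

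The unmatched constant gives 4.78, rounded up to 5, which is the plan's figure. The matched constant gives 5.78, rounded up to 6. Because the trial is matched, 6 is the reference below.

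**2. Degrees of freedom.** Four sites, less one for the intercept, one for the pair indicator and one for arm, leave 1 for between-site variance. Ignoring the matching would leave 2.

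**3. What the pilot CV would look like if the true value is 0.15.** With 40 per clinic, a pair difference has

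- binomial variance 0.4516/40 = 0.01129
- between-clinic variance 0.01729
- total 0.02858

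The moment estimate of k² is the observed variance of the two pair differences minus the binomial part, divided by the sum of squared proportions and floored at zero.

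- It is zero when a 1-df chi-square variable falls below 0.01129/0.02858 = 0.395, which has probability 2Φ(0.628) − 1 = 0.47.
- Its 97.5th percentile is about √[(5.024 × 0.02858 − 0.01129)/0.7684] = 0.41.

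A simulation of 200,000 pilots agrees: 47% zeros, median 0.045, central 95% range 0 to 0.42, and 20% of estimates between 0.10 and 0.20. Beta-distributed clinic effects give nearly the same (46% zeros, upper limit 0.43). Ignoring the matching still gives 32% zeros and a range of 0 to 0.36.

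**4. RCT size if that estimate alone were used** (matched constant, m = 75, rounded up):

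| CV used | Clusters per arm |
|---|---|
| 0 | 3 |
| 0.10 | 5 |
| 0.15 | 6 |
| 0.20 | 8 |
| 0.25 | 11 |
| 0.30 | 15 |

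Over the simulated pilots the central 95% range is 3 to 26, and 17% land within one cluster of 6. In 57% the resulting RCT would have true power below 60%. In about 14% it would be at least twice the needed size.

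**5. Other true values** (normal clinic effects):

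| True CV | Needed per arm | Estimated as zero | 95% range of size | Within one cluster |
|---|---|---|---|---|
| 0.10 | 5 | 55% | 3 to 17 | 23% |
| 0.20 | 8 | 39% | 3 to 37 | 12% |
| 0.25 | 11 | 34% | 3 to 53 | 8% |

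**The case against.** **A pilot may be small, and nothing in this one turns on the CV.** The second part stands: the only feasibility rule is a 22% difference in engagement in care. A reader might infer that the go/no-go decision is compromised by a noisy CV. The plan does not support that. The pilot's size does not rescue the stated aim, however, because the CV is one of only two parameters named.

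**The plan does not say that the pilot CV will replace 0.15.** This also stands. The sentence on sample size refers to the analyses collectively and does not name the CV. A reader might infer that the RCT will be missized. The text supports only that it could be, if the pilot estimate were used alone.

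**The textbook interval overstates the uncertainty.** Chi-square limits for an SD on 1 df run from 0.45 to 31.9 times the estimate. Applied to 0.15, the upper limit is 4.8, but a proportion averaging 0.5 cannot have a CV above 1. Those limits also assume a directly observed SD, with no binomial noise to remove. The simulated range is the better guide, and it is wide enough.

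**The 56-clinic figure may not be as good as it looks.** Its outcome and population are not visible in the text available, and the Background describes ART OPTI as an evaluation of dolutegravir scale-up. Its precision depends on how it was derived. Ignoring sampling error within clinics, the limits are about 0.84 to 1.23 times the estimate on 55 df, or about 0.79 to 1.36 if it came from 28 pairs (an assumption). Either is far tighter than 1 df, but transfer to PWID who are out of care is not shown.

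**Conclusion.** The point holds as a fault in a stated aim. The plan says the pilot will measure the CV for RCT sizing, and its design leaves 1 df for that quantity. If the true CV is 0.15, nearly half of pilots would report zero, and the 95% range of estimates runs to about 0.42. Sizing on that estimate alone would give 3 to 26 clusters per arm, against 6.

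These figures assume 50% vs 72%, 40 patients per pilot clinic, 75 per RCT cluster, two-sided 0.05 and the matched-pair constant. The conclusion is the same for true CVs from 0.10 to 0.25 and for normal or beta clinic effects.

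The consequence for the RCT is conditional on use of the pilot CV without the existing estimate. The pilot's procedures and feasibility rule are not affected.

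**What to change.** - **Study Design:** remove the CV from the parameters the pilot measures for sizing. Alternatively, label it descriptive and report the spread of the two pair differences with its 1-df uncertainty.
- **Statistical Analysis and Feasibility Assessment:** state that the RCT's CV will come from multi-clinic data. The starting point is the 56-clinic ART OPTI estimate, with its outcome and population stated. Where possible, check it against an MIS extract among PWID over clinics that meet the site criteria.
- **RCT sizing:** present the required clusters over a range of CV, for example 0.10 to 0.25, which gives about 5 to 11 per arm under the planning values above.

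The extract would be a proxy. Clinics outside the trial have no enrolment date, so a start date such as the missed visit would be needed. The Aim 1 matching factors will not be available for all of them, so the extract would not give a true within-pair CV.

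The cost is wording in two sections and, if done, one extract that needs the agreement of the MIS owner and some analyst time. Pilot sites, patients and procedures do not change.
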